**Emory University Investigator**

[name], Assistant Professor of Medicine, Department of Cardiology

**Introduction/Background:** Catheter ablation of cardiac arrhythmia is performed to offer symptomatic relief from a variety of atrial, ventricular and atrio-ventricular rhythms. Irrigated ablation catheters are commonly used for ablation of arrhythmias arising from the left heart and coronary sinus, to mitigate potentials risks of catheter ablation, including char formation on the catheter tip. These catheters contain internal channels allowing for infusion of an external fluid directly to the tip of the catheter, where the fluid is sprayed through numerous end holes allowing for cooling of the catheter ablation tip. Normal and half normal saline are the most commonly used irrigant fluids.

Fluid filled catheters are also the primary tool utilized to assess intravascular and intracardiac pressures and hemodynamics in the cardiac catheterization suite and intensive care unit. Intravascular hemodynamics allow assessment and diagnosis of a variety of cardiac conditions which are commonly found in patient undergoing catheter ablation, including congestive heart failure, diastolic dysfunction, and valvular heart disease. However, the fluid filled catheters commonly used for these assessments are single lumen and generally have a minimal diameter of 5 French for intracardiac catheters. Principles of fluid mechanics are characterized by Poiseuille's law and Bernoulli's law, which suggest that the radius of the fluid filled catheter will impact the reliability of the reading. "Dampening" of pressure waveforms are observed in smaller diameter catheters and may lead to underestimation of peak pressure and overestimation of the nadir pressure gradient.

It is unknown if transduction of pressures from the tip of an irrigated ablation catheter will yield equivalent results compared to use of a single 5F lumen catheter.

The purpose of this study is to test the hypothesis that transduction of intracardiac pressures using an irrigated ablation catheter placed as standard of care for the ablation procedure is equivalent to transduction of pressures using a standard 5F balloon tipped PA catheter placed only for this research study.

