### **Objectives:**

The main objective of this study is to take intracardiac pressure measurements and pressure waveforms with both a "gold standard" balloon tipped pulmonary artery catheter placed for this study and an irrigated ablation catheter placed as standard of care for the procedure in order to evaluate the following 2 questions:

1. Determine accuracy of intracardiac pressure measurements as assessed by the balloon tipped pulmonary artery catheter and by an irrigated ablation catheter.
2. Determine accuracy of intracardiac pressure waveforms measured by the balloon tipped pulmonary artery catheter and by an irrigated ablation catheter.

**Research Design:** The study will occur in patients undergoing routine cardiac ablation of his/her arrhythmia with planned use of an irrigated ablation catheter. The irrigation port of the irrigated ablation catheter will be connected via a three way stop cock to the irrigation tubing via 1 port and to a pressure transducer via the second port (see figure 1). All ports will be flushed through to the tip of the catheter to ensure no air in the line, per standard protocol. The pressure transducer will be leveled and “zeroed” per routine using CARDIOLAB software. A 5F MPA catheter will be prepared in similar fashion to the ablation, without an irrigant line running. “Zero” will be confirmed by positioning each catheter next to each other and assessing for equal waveform values.

Ablation and catheter manipulation will be done per routine under the supervision of a qualified electrophysiologist. The pressure line will be left “off” with the stopcock during the EP study and ablation, and whenever pressure assessment is not being performed.

After completion of ablation/study, the ablation catheter will be serially positioned in the cardiac chambers (left OR right atrium, left OR right ventricle). Because pressure values, slopes and characteristics are similar between the atria and ventricles, all 4 chambers will not be sampled. The stop cock will be turned to the pressure transducer and waveforms will be stored corresponding to each chamber. Next, the catheter will be removed and replaced with a 5F balloon tipped PA catheter which will be positioned under fluoroscopic guidance in each previously evaluated chamber. The placement of the balloon tipped PA catheter and measurements for this study will take about 10 additional minutes.

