**Informed Consent:** Following education on the study protocol, patients will be offered the option to enroll. Informed consent will be obtained by approved research personnel in a private area. If the patient agrees to participate, consent will be documented. Consent will occur the day of the scheduled ablation procedure.

**Compensation for time and effort:** There is no compensation for participation in this study. This research will add about 10 minutes to the standard of care procedure. .

**Data analysis:** The systolic, diastolic and mean pressure values for each chamber assessed will be compared between the RF ablation catheter derived measurement and the MPA catheter measurement. Measurements will be made in duplicate for each value. Comparison will be made using T – Test and a Kappa statistic.

Waveforms will be compared using a MACLAB system, by determining a mean gradient between the two waveforms. These values will be compared using a T –Test. All analyses will be performed using Microsoft Excel and Graphpad Prism.

**Safety:** Positioning of both catheters (ablation catheter and PA catheter ) will be done under continuous ultrasound guidance to ensure positioning of the catheter without secondary damage to the heart, heart valves or heart muscle. Fluoroscopy and 3-dimensional computer mapping will be used or immediately available for use in assisting positioning when needed. All catheter manipulation will be done by an experienced, Board certified cardiologist with greater than 10 years of experience in PA catheter manipulation and positioning [name].

The tip of the PA catheter has a balloon which will be inflated whenever advancing the balloon forward. This reduces risk of perforation as the catheter will bounce off the walls of the heart when encountered.

The catheter will be primarily position with use of guiding catheters which are already position in the chamber of interest(s) for the purpose of the catheter ablation procedure itself. This will also help minimize risk and time associated with PA catheter manipulation.

Equipment necessary to treat potential complications of catheter manipulation such as fluid or bleeding around the heart will be immediately available in the procedure suite. Operators will be experienced and qualified to perform stabilizing and treating procedures in case of such emergency.

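### No planned comparison isolates the damping that the protocol predicts: offset can mask it in either the systolic or the diastolic test, and shifts between readings add noise to both

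*Combined protocol and SAP*

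**What the plan says.** Introduction/Background gives the mechanism by which a small-bore fluid line may misread: damping "may lead to underestimation of peak pressure and overestimation of the nadir pressure gradient". The hypothesis there is that transduction through the irrigated catheter "is equivalent to transduction of pressures using a standard 5F balloon tipped PA catheter placed only for this research study". Objectives asks two questions, one on pressure values and one on waveforms.

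Data analysis then sets the comparisons. "The systolic, diastolic and mean pressure values for each chamber assessed will be compared between the RF ablation catheter derived measurement" and the reference catheter's value, with duplicate measurements. "Comparison will be made using T – Test and a Kappa statistic". Whether the t-test is paired is not stated, and no categories are given for kappa. Waveforms are compared "by determining a mean gradient between the two waveforms", again with a t-test; whether the gradient is signed or absolute is not stated. No comparison combines systolic with diastolic, and no rule says how the separate results are to be read together.

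Research Design takes steps against offset. "The pressure transducer will be leveled and" zeroed in the routine way, and the zero "will be confirmed by positioning each catheter next to each other and assessing for equal waveform values". No tolerance is given. Chamber readings are taken first with the ablation catheter. "Next, the catheter will be removed and replaced with a 5F balloon tipped PA catheter", so the two sets of readings are sequential. Patient selection aims for at least 10 usable datasets from up to 15 patients.

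**The concern.** Two kinds of error can separate the catheters, and they leave different signatures. Damping pulls peak and nadir toward each other. A level or zero error, or a genuine change in the patient's pressure between readings, moves them together. Each planned pressure test sees a mixture of the two, and the contrast that would separate them is not analysed, although both of its components are collected.

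Two things are at stake. If a fixed offset remains, a systolic or diastolic result may be put down to the wrong cause: an offset could be levelled out, whereas lost amplitude could not. If there is no fixed offset but pressure drifts at random between readings, that drift inflates the variance of both differences, and modest damping may be missed in a study of about 10 patients. The second objective, on waveforms, is the most exposed, because loss of amplitude is the distortion that the protocol itself predicts.

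**Working it through.** **Signs.** Let each difference be ablation catheter minus reference, with offset or shift b and damping dS, dD > 0:

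- systolic = b − dS
- diastolic = b + dD
- mean ≈ b
- systolic minus diastolic = −(dS + dD), free of b

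If b is positive it opposes damping in the systolic test and adds to it in the diastolic test; if b is negative, the reverse. This needs no outside figure.

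**Does the waveform analysis fill the gap?** A first-order low-pass filter (time constant 0.02 s) was applied to an assumed ventricular-type waveform. Values are in mmHg:

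| Offset | Systolic | Diastolic | Signed mean gradient | Mean absolute gradient | Systolic minus diastolic |
|---|---|---|---|---|---|
| 0 | −3.05 | +0.65 | 0.00 | 5.57 | −3.69 |
| +3.05 | 0.00 | +3.69 | +3.05 | 7.35 | −3.69 |
| −0.65 | −3.69 | 0.00 | −0.65 | 5.89 | −3.69 |

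A signed gradient follows the offset and not the damping. An absolute gradient mixes the two.

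**Power with random shift and no fixed offset.** The plan gives no alpha, SD, effect size or power, so there is no figure of its own to reproduce. Only n = 10 comes from the documents. The assumptions are:

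- paired t-test, two-sided 5%
- pressure 25/5 mmHg, so amplitude 20
- 10% amplitude loss split equally, so dS = dD = 0.10 × 20 / 2 = 1 mmHg
- shift SD 2.5 mmHg
- noise SD 0.7 mmHg per reading, so difference variance 2 × 0.49 = 0.98
- variation in the amplitude difference between readings with SD p × 20, split equally between peak and nadir

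Then:

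- SD(systolic) = SD(diastolic) = √[2.5² + 0.98 + (20p)²/4]
- SD(systolic minus diastolic) = √[2 × 0.98 + (20p)²]
- power comes from the noncentral t with 9 degrees of freedom and noncentrality √10 × |difference| / SD, where the difference is 1 mmHg for systolic or diastolic and 2 mmHg for the contrast

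| p | SD, systolic or diastolic | Power, each | SD, contrast | Power, contrast |
|---|---|---|---|---|
| 5% | √7.48 = 2.73 | 18% | √2.96 = 1.72 | 90% |
| 10% | √8.23 = 2.87 | 17% | √5.96 = 2.44 | 64% |
| 15% | √9.48 = 3.08 | 15% | √10.96 = 3.31 | 40% |

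The mean-pressure test stays at 5%. At p = 5%, simulation puts the chance that at least one of the three planned pressure tests is significant at about 36%.

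Sensitivity:

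- With shift SD 1 mmHg and p = 5%, SD(systolic) = √(1 + 0.98 + 0.25) = 1.49. Systolic power rises to about 47%, against 90% for the contrast.
- If pulse variation applies to each catheter's reading separately, its variance doubles. The contrast SD becomes √(1.96 + 2) = 1.99, √(1.96 + 8) = 3.16 and √(1.96 + 18) = 4.47, and its power about 81%, 43% and 24%.

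**Fixed offset of +2 mmHg, same SDs, p = 5%.**

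- 25/5 mmHg with 20% loss: dS = dD = 2. The systolic difference is 2 − 2 = 0 (power 5%). The diastolic difference is 2 + 2 = 4 mmHg (98%). Mean pressure has about 56%, and the contrast about 100%.
- 120/10 mmHg with 5% loss: dS = dD = 0.05 × 110 / 2 = 2.75. Systolic is 2 − 2.75 = −0.75 (about 7% to 8%). Diastolic is 2 + 2.75 = 4.75 (about 81% to 93%). The contrast is 5.5 mmHg, with SD √(1.96 + 30.25) = 5.68 or, with per-reading variation, √(1.96 + 60.5) = 7.90 (about 78% or 50%).
- 25/5 mmHg with no damping: systolic is significant in about 53% to 54% of studies, the contrast in 5%.

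**The case against.** The strongest reply is that the planned set of tests already detects the problem. Offset and damping cannot cancel in both tests at once. In the +2 mmHg cases above, the diastolic test rejects in 98% and in about 81% to 93% of studies, and in the second case more often than the proposed contrast. A reader might infer that an offset could let a damped catheter pass the whole analysis. The documents do not support that: where a fixed offset hides damping in one test it enlarges the other, so what is at risk is the attribution of cause. This part of the reply stands.

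Second, Research Design zeroes the line and compares the catheters side by side, so a lasting 2 mmHg offset is an assumption and not something the documents show. That also stands. With no offset, the systolic and diastolic tests each measure damping directly. But the check has no tolerance and cannot remove a pressure change between sequential readings, and it is the random shift that drives the power loss.

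Third, the contrast can be read by subtracting the two reported mean differences. True for the point estimate, but its confidence interval cannot be recovered from the separate results, because the paired systolic and diastolic differences are correlated.

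Fourth, a catheter that reads high is inaccurate whatever the cause. That answers the first objective but not the second, which concerns the waveform.

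Finally, a reader might take the contrast to be immune to every change between readings. It cancels only shifts that move peak and nadir equally. A change in stroke volume, rhythm or loading alters amplitude itself, which is why the advantage shrinks as pulse variation grows.

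**Conclusion.** The point holds as a gap in the analysis, not in the data. No planned comparison isolates the predicted damping. A fixed offset can mask it in one of the systolic and diastolic tests, mainly leading to misattribution; random shifts between readings can cause modest damping to be missed.

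The algebra rests on the protocol's own description of damping and on shifts that move peak and nadir equally. The size is illustrative. At 25/5 mmHg, 10% loss, 10 patients and shift SD 2.5 mmHg, each planned systolic or diastolic test has about 15% to 18% power, against 90%, 64% and 40% for the contrast. The contrast exceeds each single planned test in every 25/5 mmHg setting with 10% loss tried here, but by an amount that depends on assumed SDs and on how pulse variation is modelled. In the 120/10 mmHg case with offset it does not beat the diastolic test. This is a cheap improvement for the authors to consider, and it does not undermine the study.

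**What to change.** In Data analysis, define pulse amplitude as systolic minus diastolic for each patient, chamber and catheter. Report the paired between-catheter difference with a 95% confidence interval as the damping result. Use mmHg as the default scale, and the log ratio only for ventricular readings, because atrial amplitudes are small and a ratio would be dominated by noise. Present it beside the paired systolic, diastolic and mean differences, and state that the mean difference is read as the offset result. State also whether the waveform gradient is signed or absolute, so that a reader knows what it responds to.

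The cost is one derived variable from values already collected and a few sentences. The downsides are one more comparison in a small study, whose place among the others should be stated in advance, and the need to say that the contrast removes only shifts common to peak and nadir.

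### One equivalence hypothesis is judged by about 8 t-tests and 6 kappas, with no primary comparison and no rule for combining them, so a mixed result could be reported either way.

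*Combined protocol and SAP*

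**What the plan says.** The Introduction/Background states a single hypothesis: pressure transduction through the ablation catheter "is equivalent to transduction of pressures using a standard 5F balloon tipped PA catheter". It warns that narrow catheters damp the waveform, so that peaks read too low and troughs too high.

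Objectives says that both sets of readings are taken "in order to evaluate the following 2 questions", one on pressure measurements and one on waveforms. Neither is ranked above the other.

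Under Research Design the catheter is "serially positioned in the cardiac chambers (left OR right atrium, left OR right ventricle". The same paragraph says that "all 4 chambers will not be sampled", because atrial and ventricular pressures are regarded as similar on the two sides. Each patient therefore contributes one atrium and one ventricle.

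Under Data analysis, "The systolic, diastolic and mean pressure values for each chamber assessed will be compared" between catheters, using a t-test and a kappa, with duplicate readings. For waveforms, a mean gradient between the two tracings is determined, and "These values will be compared using a" t-test. The section then names the software and ends. It gives no primary comparison, significance level, equivalence margin, kappa threshold, multiplicity rule or rule for disagreeing results.

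**The concern.** Several statistics bear on one conclusion, and the plan does not say which of them decides it. If any significant t-test counts as inaccuracy, a catheter that agrees perfectly will fail too often. If non-significant tests count as support for equivalence, a biased catheter can be partly cleared by the comparisons least sensitive to its fault. The reading can then be chosen after the results are seen.

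The protocol's own failure mechanism makes this concrete. Damping pushes systolic and diastolic readings in opposite directions. The errors can offset in mean pressure, and in the mean gradient if it is signed. The study would then report that two kinds of comparison differ and two do not, and nothing in the plan says what that means for the hypothesis. Patients undergo a research-only catheter placement to answer this question, so the reading should be fixed beforehand.

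**Working it through.** The plan states no number of tests, significance level or power, so it has no figure to reproduce.

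**Inputs from the plan.** Three pressures per chamber (Data analysis); one atrium and one ventricle per patient (Research Design); at least 10 usable datasets from up to 15 patients (Patient selection).

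**Assumptions.** Two-sided 0.05 per test; paired t-tests; duplicates averaged; one gradient per chamber, tested against zero; left and right sites pooled within chamber type; n = 10. Correlations between differences (within chamber, between chambers) are (0, 0), (0.5, 0.2) and (0.7, 0.3).

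**Step 1, count.**
- t-tests: 3 pressures x 2 chambers + 1 gradient x 2 chambers = 8.
- kappas: 3 pressures x 2 chambers = 6.

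**Step 2, no true difference.** With independent tests, P(at least one significant) = 1 - 0.95^8 = 1 - 0.663 = 0.337. In 20,000 simulated studies at the three correlation settings the figure is 34%, 29% and 25%. All eight are non-significant in the remaining 66-75%.

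**Step 3, damping.** Let the systolic difference be -b and the diastolic +b, with mean pressure and mean gradient unchanged (full cancellation, an assumption). At b = 1 SD and n = 10, the power of one paired t-test is 0.803 (noncentral t, 9 df, noncentrality 1 x √10 = 3.16). Four of the eight tests carry the bias and four carry none. With independent tests:
- none significant: (1 - 0.803)^4 x 0.95^4 = 0.0015 x 0.8145 = 0.0012;
- all significant: 0.803^4 x 0.05^4 = 0.416 x 0.00000625, which is negligible;
- mixed: 1 - 0.0012 = 0.9988.

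Simulation at all three correlation settings, for b = 1, 1.5 and 2 SD, gives mixed results in over 99% of studies. A larger bias does not resolve the ambiguity, because four of the tests have nothing to detect.

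**Step 4, the same bias in every comparison.** This shows where the problem is smaller.

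| Truth (n = 10, 8 t-tests) | Mixed significant and non-significant |
|---|---|
| No bias | 25-34% |
| 0.8 SD in every comparison | 77-98% |
| 1.5 SD in every comparison | 7-10% |
| Damping, 1-2 SD, full cancellation | over 99% |

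The kappas are left out of these figures because the plan gives no categories or threshold from which to calculate.

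**The case against.** Four objections deserve an answer.

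*The ambiguity is not universal.* A reader might infer that almost any data could be reported either way. The figures do not support that. With no bias the eight tests all agree in most studies, and with a uniform 1.5 SD bias they are all significant in about 90% or more. The 77-98% row is not a general figure either: it belongs to a 0.8 SD bias in every comparison at n = 10, and at n = 15 the same bias gives 53-79%. A uniform bias is also not the pattern that the Introduction predicts.

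*The count could be set higher or lower.* A reader might double it by testing left and right chambers separately. The plan never says so, and its reason for not sampling all four chambers points towards two chamber types. Nor could 10 patients be had in each of four chambers: with one atrium and one ventricle each, at most 15 patients cannot supply 10 left and 10 right sites of either type. The two gradient tests also answer the second study question rather than the first. Even so, six pressure t-tests remain for the first question: 1 - 0.95^6 = 0.265 if independent, again with no combining rule.

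*A split result would be informative.* Systolic and diastolic differing while the mean agrees is the signature of damping, and an expert might read it correctly. That stands as interpretation. It does not settle whether the catheters are then called equivalent.

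*The missing margin is the deeper gap.* This is right. A non-significant difference test cannot show equivalence, so naming one primary t-test would not repair the plan. But a margin alone does not say which comparisons must meet it. The two gaps need to be closed together.

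**Conclusion.** The concern holds in this limited form: one equivalence hypothesis, about 8 t-tests and 6 kappas, and no primary comparison or combining rule. With no true difference, 25-34% of studies would show at least one significant t-test. Under the damping the protocol itself describes, a mixed result is the expected outcome. The figure of over 99% rests on full cancellation in the mean and the gradient, which is not established; the plan does not say whether the gradient is signed, and an unsigned one would not cancel. All figures also rest on the assumed significance level, paired testing, averaged duplicates and correlations.

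This is more than a missing detail, since the plan could be followed exactly and still leave the conclusion to choice. It should be corrected before the data are analysed, but it does not make the measurements unusable.

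**What to change.** In Data analysis:

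- Name systolic and diastolic pressure as co-primary for the first question, since these are the readings that damping distorts.
- For each chamber type, conclude equivalence only if, for both values, the 90% confidence interval of the paired mean difference lies within a prespecified margin in mmHg (two one-sided tests at 0.05). The investigators set the margin. State how the duplicates enter the difference.
- Claim overall equivalence only if the atrial and the ventricular sites both pass. Otherwise limit the claim to the chamber type that passed.
- Report mean pressure, the waveform gradient (second question) and any kappa as secondary estimates with 95% confidence intervals and no significance verdict.

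The overall claim needs no alpha split, because every component must pass. A claim limited to one chamber type has two chances to arise, so it should be reported as such (1 - 0.95^2 = 0.0975 at most if the two are independent).

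The cost is a few sentences and a justified margin, with no added patients or procedures. The downside is that an overall equivalence claim becomes harder to reach. The documents give no SD for the paired differences, so whether 10 to 15 patients can meet a given margin cannot be calculated from them.

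### For duplicate readings by both catheters in the same patient, the plan names only a t-test and leaves pairing, use of the duplicates and unit of analysis open

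*Combined protocol and SAP*

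**What the plan says.** Under Research Design, one atrium and one ventricle are sampled: "the ablation catheter will be serially positioned in the cardiac chambers (left OR right atrium, left OR right ventricle". The ablation catheter is read first. It is then "replaced with a 5F balloon tipped PA catheter which will be positioned under fluoroscopic guidance in each previously evaluated chamber". Each patient is therefore their own control, chamber by chamber.

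The Data analysis paragraph sets systolic, diastolic and mean pressure in each chamber to be "compared between the RF ablation catheter derived measurement and the MPA catheter measurement". It continues: "Measurements will be made in duplicate for each value. Comparison will be made using T – Test and a Kappa statistic". On software it says "All analyses will be performed using Microsoft Excel and Graphpad Prism", which does not settle the form of the test.

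Patient selection gives up to 15 patients, to yield at least 10 usable datasets. The Introduction states the hypothesis as equivalence. The documents give no alpha, SD, effect size or margin. No section says whether the t-test is paired, whether duplicates are averaged, entered separately or modelled, or what counts as one observation.

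**The concern.** A t-test on these data can be run in several ways, and they do not agree.

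- **Unpaired.** Differences in pressure from patient to patient, which the design removes, go back into the error term. In most trials an inefficient test works against the investigator. Here the hypothesis is equivalence, so a non-significant result is easily taken as support. The Introduction itself expects a bias in smaller catheters, with peaks read too low and nadirs too high.
- **Paired, with each duplicate as a separate row.** Each patient counts twice. The confidence interval is too narrow and the test rejects too often.

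With 10 to 15 patients, this choice can decide the conclusion. The duplicates also have no stated use, although they could show how repeatable the readings of each catheter are.

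**Working it through.** There is no planned figure to reproduce, because the sample size comes without a calculation. All values in mmHg below are assumptions.

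**Inputs.** From the documents: n = 10 (minimum usable) or 15 (maximum enrolled), two catheters per patient, two readings per value. Assumed: two-sided alpha 5%, true bias 3, SD of the patient-level difference 3, between-patient SD s from 2 to 15.

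**1. Paired test, one difference per patient, n = 10.** SE = 3/√10 = 0.949. The critical t on 9 df is 2.262, so the confidence-interval half-width is 2.262 × 0.949 = 2.15. The noncentrality is 3/0.949 = 3.16, which gives power of about 80%. For n = 15 it is about 95%. Neither figure depends on s.

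**2. Unpaired test on the same values.** The SE used is √[2(s² + k)/n]. The term k depends on what s means:

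- k = 9/2 = 4.5 if s is the SD of a patient component common to both catheters, with independent catheter deviations.
- k = 9/4 = 2.25 if s is the SD of each patient's average over the two catheters, independent of the difference.

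The critical t on 18 df is 2.101. The observed mean difference must exceed about 2.101 × SE, while its actual SE stays at 0.949 around a true value of 3. Power is by simulation.

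| s | SE (k = 4.5) | threshold | power, k = 4.5 | power, k = 2.25 |
|---|---|---|---|---|
| 2 | 1.30 | 2.74 | 62% | 75% |
| 3 | 1.64 | 3.45 | about 38% | 47% |
| 5 | 2.43 | 5.10 | 8% | 10% |
| 8 | 3.70 | 7.78 | under 1% | under 1% |
| 15 | 6.77 | 14.23 | about 0% | about 0% |

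With n = 15 and k = 4.5, the unpaired figures are about 84%, 63%, 17%, 1% and 0%, against 95% paired.

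**3. Paired test with duplicates as 2n rows.** Let r be the correlation between a patient's two differences. The variance of the mean is σ²(1 + r)/(2n), but the test uses σ²/(2n). The true SE is thus √(1 + r) times the SE used: 1.14, 1.22, 1.34 and 1.40 for r = 0.3, 0.5, 0.8 and 0.95. Simulated type I error is about 8.5%, 11%, 15–16% and 17–18%, with similar values at n = 10 and n = 15.

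**4. A second set of assumptions.** Take n = 10, bias 4, patient-level difference SD 3 and repeat-reading SD 1. Power falls from 0.94 (paired means) to 0.24 (unpaired means) at s = 5 and to 0.01 at s = 10. Paired duplicate rows give a type I error of about 0.15–0.16, and the interval half-width shrinks from 2.2 to 1.5.

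**5. A mixed model with only a patient random effect.** It treats the two readings within a catheter as independent, so it keeps the error of step 3. With s = 8, difference SD 3 and repeat SD 1, 2 or 3, the simulated type I error is about 23%, 16% and 11% at n = 10, and 22%, 15% and 11% at n = 15.

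**The case against.** The plan is silent; it does not choose the wrong test. The design points to pairing: the second catheter goes into the chambers already sampled, enrolment is counted in comparison datasets, and the waveforms are reduced to a mean gradient that is already a within-patient difference. The words "Comparison will be made using T – Test and a Kappa statistic" may well mean a paired test. All of this stands. A reader might infer that the plan specifies an unpaired test, or has decided to ignore the duplicates. The documents support neither.

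A reader might also infer that both harms occur together. They need opposite readings of the same sentence. The 8–18% type I error arises only if the analyst pairs. If all readings go into an unpaired test, the second set of assumptions gives null rejection of 2% or less at a between-patient SD of 5 and above, and 4–9% at an SD of 2.

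The loss of power is modest if patients differ little, and one set of SDs cannot stand for three pressures in two kinds of chamber. That also stands, which is why the range starts at 2 mmHg.

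"Measurements will be made in duplicate for each value" does not say whether a duplicate is a second acquisition or a second reading of one stored trace. In the latter case it shows reading error and not catheter repeatability.

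Finally, even a correct paired t-test tests only for a difference. Non-significance could still be misread as equivalence, because no margin is given. That gap, and the use of kappa on continuous pressures, are separate issues. Resolving them would not resolve this one, since an equivalence test needs the right standard error too.

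**Conclusion.** The point holds as under-specification with consequences. The data are paired and clustered within patient, and the plan leaves open analyses that err in opposite directions. The direction of each error follows from the design. The sizes rest on assumed values (bias 3 mmHg, difference SD 3 mmHg, 10 patients), which the documents neither give nor contradict. Under these, leaving out the pairing costs little to moderate power if patients differ by an SD of 2–3 mmHg and nearly all of it at 8 mmHg or more. Counting duplicates as independent pairs raises type I error to between about one and a half and three and a half times the nominal 5%. The point concerns the pressure values; the waveform gradient is largely unaffected. The plan should be changed on this before data are analysed.

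**What to change.** In the Data analysis paragraph, replace the t-test for the pressure values with:

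> For each chamber and each pressure, average the duplicates within patient and catheter, form one ablation-minus-reference difference per patient, and report the paired mean difference with its 95% confidence interval and limits of agreement, n = number of patients.

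Add what a duplicate is. Report the within-patient SD of each catheter from the duplicates, and call it catheter repeatability only if they are separate acquisitions.

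If a mixed model is preferred, it needs both patient and patient-by-catheter random effects; a patient effect alone does not solve the problem.

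The cost is a few sentences and a few spreadsheet columns. No extra patients, readings or procedure time are needed, and the software already named is enough for the averaged, paired analysis.
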